6.2 Collection, Recording and Reporting of Adverse Events

An appropriate member of the research team will record all directly observed AEs and all AEs reported by the trial participant up to six months following their trial treatment.

In addition, sites should follow their own local procedures for the reporting of any adverse events linked to clinical care.

All AEs requiring reporting will be recorded on an (S)AE form or REDCap data collection tool and will be reported to YTU according to the agreed timelines.

The severity and likely relationship to study treatments of any adverse events will be documented by the designated site clinician.

An event is defined as 'related' if the event was due to the administration of any research procedure. Whereas an 'unexpected event' is defined as a type of event not listed in the protocol as an expected occurrence.

All non-serious AEs whether expected or not, should be recorded in the participant's medical notes.

Related and unexpected AEs will be recorded on the study AE data collection tool by the research staff and sent to YTU within an agreed timescale (usually five days). SAEs should be notified to the Principal Investigator and to YTU within 24 hours of the research staff or clinical team becoming aware of the event.

At the time of reporting, the PI or delegated clinician will be asked to record an assessment of causality (to trial treatment) selecting an option from the list below:

- Definitely related- there is clear evidence to suggest a causal relationship, and other possible • contributing factors can be ruled out.
- Probably related- there is evidence to suggest a causal relationship, and the influence of other factors is unlikely
- Possibly related- there is some evidence to suggest a causal relationship (e.g. the event • occurred within a reasonable time after administration of the trial procedures). However, the influence of other factors may have contributed to the event (i.e. the participant's clinical condition, other concomitant events).
- Unlikely to be related- there is little evidence to suggest there is a casual relationship (e.g. • the event did not occur within a reasonable time after administration of the trial procedures). There is another reasonable explanation for the event (e.g. the participant's clinical condition, or other concomitant treatments).
- Unrelated- there is no evidence of any causal relationship.

Once received, causality and expectedness will be confirmed by the Chief Investigator. SAEs that are deemed to be unexpected and related to the trial will be notified to the Research Ethics Committee (REC) and Sponsor within 15 days.

All such events will be reported to the Trial Steering Committee and Data Monitoring Committee at their next meetings. All participants experiencing SAEs will be followed up as per protocol until the end of the trial.

General surgical complications Deep wound infection Superficial infection Bleeding /haematoma Suture abscess Surgical site infection Rehospitalisation Delayed wound healing / wound dehiscence Unexplained pain Tourniquet related nerve injury **Anaesthetic-related complications** Myocardial infarction (MI) Block related nerve lesion Cerebrovascular accident (CVA) Venous thromboembolism (VTE) Local anaesthetic toxicity Complications specific to flexor tendon repair surgery Digital nerve injury / neuroma / numbness / **Tendon adhesions** altered sensation Re-rupture of tendon repair Cold intolerance Complex regional pain syndrome Bow stringing Joint stiffness Hand Therapy-related Complications Skin problems related to splint fitting

Table 9: Expected complications associated with flexor tendon repair surgery

7. Research Governance

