4.5.2 Participant Exclusion Criteria (at screening)

- Injuries affecting more than one digit or the thumb
- Injuries outside of Zone 2
- Injuries affecting multiple zones
- Clinically infected wounds
- Closed flexor tendon injury
- Previous tendon, bone or joint injury in the affected digit
- Patient does not have capacity to give informed consent
- Patient unable to complete follow up requirements
- Contraindication to surgery

Exclusion criteria for randomisation (confirmed at surgery)

- Injuries with loss of tendon substance or skin necessitating reconstruction
- Division of both digital arteries resulting in revascularisation of injured digit
- Division of both digital nerves

Injuries are restricted to zone 2 as it is the most common injury and most challenging to manage owing to both tendons running in the flexor sheath.

Unilateral digital nerve injuries will be accepted on a pragmatic basis as they are often injured in addition to the flexor tendon. A recent study suggests digital nerve injury does not affect the outcome of zone 2 flexor tendon injuries [23].

Thumb injuries are excluded owing to the anatomy. There is a single thumb flexor tendon, and flexor sheath anatomy differs to the fingers. The rehabilitation regimen also differs.

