4.6.1 Surgical Intervention

Study treatments should be given as soon as practical following recruitment. The timing of treatment is determined by local service pressures, however standard care is to surgically explore the wound and repair the tendons within 72 hours of presentation.

Surgical exploration and washout will be undertaken for all consenting patients. Patients that are confirmed as eligible during surgery will be allocated to receive either FDP repair alone or repair of both FDP and FDS.

A minimum 4 strand core suture will not be mandated but the number of strands will be recorded. A 4-strand core repair is standard practice for 80% of surgeons in the UK. An epitendinous suture (a suture around the outside edge of the tendon) will not be mandatory but if done will be recorded. Suture choice and technique will be pragmatic. Intraoperatively, surgeons will ensure excursion of the repaired tendon(s) through a full range of movement. Tendon sheath and pulleys will be released as needed to allow unimpeded gliding. Concomitant single digital nerve injuries will be repaired.

Choice of anaesthetic will be pragmatic and based on patient and surgeon preferences and availability.

Post-operative care will be in line with routine practice at the participating site. Usually, the wounds will be dressed and a plaster of Paris dorsal blocking splint applied.

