6.1 Definitions

An adverse event (AE) will be defined as the following: any untoward medical occurrence in a trial participant to whom a research treatment or procedure has been administered (intervention or control) and which does not necessarily have a causal relationship with the treatment. For the purposes of FLARE, we will only collect AE data for events that are related to the original finger injury and unexpected.

Complications, which might be expected with this condition and treatments, are detailed in Table 9: Expected complications associated with flexor tendon repair surgery(section 6.2) should not be reported as an adverse event. These are well known complications of surgery of which the specialist clinical care teams will be experienced in managing. These complications however will be recorded in the FLARE CRFs.

Where repeated adverse events of similar type are observed, these will be discussed with the DMC and will be onward reported to Sponsor and REC should concerns be raised in relation to the type of event and/or frequency observed.

A serious adverse event (SAE) will be defined as any untoward occurrence that:

- Results in death. •
- Is a life-threatening event (that is it places the participant, in the view of the Investigator, at • immediate risk of death).
- Requires unplanned hospitalisation or prolongation of existing hospitalisation (unplanned • refers to emergency hospitalisations resulting in an inpatient stay; prolonged hospitalisation is deemed to be where a participant's stay is longer than expected).
- Results in persistent or significant disability or incapacity (substantial disruption of one's • ability to conduct normal life functions).
- Is another important medical condition.

Version 1.1

Important medical events that may not be immediately life-threatening, result in death or hospitalisation but may jeopardise the participant or may require intervention to prevent one of the outcomes listed in the definition of an SAE will also be considered serious.

In the context of this study, SAEs will only be reported to YTU if they appear to be related to the original injury or an aspect of taking part in the study.

Other than for fatalities, this procedure does not apply to any other SAEs which may occur during the trial which are unrelated to original injury or the trial procedures.

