7.3.3 Primary Surgery Details

Data on the surgery that the participant underwent will be collected. The surgical details captured include: grade of the primary operating surgeon, background specialty, date of operation, subzone of injury, digital nerve injury, which nerve was damaged (if applicable), if the digital nerve was repaired, location of the surgical procedure, time the anaesthetic was administered, start and end time of the surgery, if the surgery was a day case, date of admission, date of discharge, type of anaesthetic used, tourniquet use, tourniquet placement, length of time tourniquet applied, antibiotic use.

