Myocardial infarction (MI)			
Block related nerve lesion			

Cerebrovascular accident (CVA)			
Venous thromboembolism (VTE)			
Local anaesthetic toxicity	-		
(all complications will be reported)	-		
Post-operative flexor tendon related complications			
1 week, n (%)	n=xxx	n=xxx	n=xxx
Digital nerve injury/ neuroma/ numbness/ altered			
sensation			
Tendon adhesions			
Re-rupture of tendon repair			
Bow stringing			
Cold intolerance			
(all complications will be reported)			
6 weeks, n (%)	n=xxx	n=xxx	n=xxx
Digital nerve injury/ neuroma/ numbness/ altered			
sensation			
Tendon adhesions			
Re-rupture of tendon repair			
Bow stringing			
Cold intolerance			
(all complications will be reported)			
3 months, n (%)	n=xxx	n=xxx	n=xxx
Digital nerve injury/ neuroma/ numbness/ altered			
sensation			
Tendon adhesions			
Re-rupture of tendon repair			
Bow stringing			
Cold intolerance			
(all complications will be reported)			
6 months, n (%)	n=xxx	n=xxx	n=xxx
Digital nerve injury/ neuroma/ numbness/ altered			
sensation			
Tendon adhesions			
Re-rupture of tendon repair			
Bow stringing			
Cold intolerance			
(all complications will be reported)			
Hand therapy related complications			
6 weeks, n (%)	n=xxx	n=xxx	n=xxx

Skin problems due to splint fitting		
Other		
(all complications will be reported)		

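### The nerve and sensation row in the complications table can include deficit from the original laceration, and Table 25 does not separate it by nerve status at surgery

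*Protocol*

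**What the plan says.** **The row.** Protocol 6.2, Table 9, places nerve injury, neuroma, numbness and altered sensation in a single entry: "Complications specific to flexor tendon repair surgery Digital nerve injury / neuroma / numbness". SAP 17.3.6, Table 25, carries it forward as "Digital nerve injury/ neuroma/ numbness/ altered" sensation, under post-operative flexor tendon related complications, at 1 week, 6 weeks, 3 months and 6 months, by arm and in total.

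**Who is eligible.** Protocol 4.5.2 states: "Unilateral digital nerve injuries will be accepted on a pragmatic basis as they are often injured in addition to the flexor tendon". The only nerve-related exclusion is "Division of both digital nerves". Under Protocol 4.6.1, "Concomitant single digital nerve injuries will be repaired".

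**How nerve status is recorded.** SAP 7.3.3 lists among the surgical data "digital nerve injury, which nerve was damaged (if applicable), if the digital nerve was repaired". SAP Table 16 tabulates nerve injury by arm as partial, complete or none.

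**How complications are handled.** Protocol 6.1 says: "Complications, which might be expected with this condition and treatments, are detailed in Table 9". It keeps these events out of adverse event reporting and records them on the CRFs. SAP 13.6 plans logistic models for complications, with covariates similar to the primary model, which adjusts for digital nerve injury (SAP 13.5). The nerve and sensation row is not among the complications named there, although the list is introduced as non-exhaustive.

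**The concern.** A patient who enters with one cut digital nerve may have a numb finger at every visit. Nothing in Protocol Table 9, SAP 7.2.11 or SAP Table 25 says whether that counts in this row. There is no new-onset or worsening rule, and Table 25 has no split by nerve status.

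This matters for three reasons.

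- Comparing the complications of the two repairs is a stated secondary objective (SAP 4.2, item d), and Protocol 1.3 names nerve damage among the surgical risks.
- The causality assessment in Protocol 6.2 is made when an adverse event is reported. Table 9 complications are not reported as adverse events, so no relatedness judgement is stated for them. A new nerve lesion and an old deficit can be recorded identically.
- Randomisation is stratified by site only (Protocol 5.5.1); the amendment history shows that digital nerve injury was removed as a factor. Nerve status is therefore balanced only in expectation.

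**Working it through.** The plan gives no figure for this row (no share with nerve injury at entry, no rate of sensory symptoms, no power), so there is nothing to reproduce. What follows is illustration on assumed inputs.

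**Share of the row due to the original injury.** Let p be the proportion with one digital nerve injured at entry, s the probability that such a patient has sensory symptoms from the injury, and q the probability of a new event in a patient without injury-related symptoms.

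Share = ps / [ps + q(1 − ps)]

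With p = 0.30 and s = 0.70, ps = 0.21 and 1 − ps = 0.79:

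| q | New events, q × 0.79 | Share from injury |
|---|---|---|
| 2% | 0.0158 | 0.21/0.2258 = 93% |
| 5% | 0.0395 | 0.21/0.2495 = 84% |
| 10% | 0.079 | 0.21/0.289 = 73% |
| 20% | 0.158 | 0.21/0.368 = 57% |
| 30% | 0.237 | 0.21/0.447 = 47% |

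Over p = 5–60%, s = 0.5–0.9 and q = 2–30%, the extremes are:

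- p = 5%, s = 0.5, q = 30%: 0.025/(0.025 + 0.2925) = 8%.
- p = 60%, s = 0.9, q = 2%: 0.54/(0.54 + 0.0092) = 98%.

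The share passes one half when p > q/[(1 + q)s]. With s = 0.7 this is 3%, 7%, 13%, 24% and 33% for q = 2%, 5%, 10%, 20% and 30%.

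**Dilution.** Assume new-event rates of 5% and 10% in the two arms, and 310 × 0.80 / 2 = 124 evaluable per arm. Approximate power is Φ(|difference|/SE − 1.96), with SE = √{[a(1 − a) + b(1 − b)]/n}.

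- Unmixed: 5% v 10%, RR 2.0, SE 0.0333, power 0.32.
- p = 20%, s = 0.7 (ps = 0.14): 0.14 + 0.05 × 0.86 = 18.3% v 0.14 + 0.10 × 0.86 = 22.6%; RR 1.23, power 0.13.
- p = 30%, s = 0.7 (ps = 0.21): 24.9% v 28.9%; RR 1.16, power 0.10.

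Restricting to patients without nerve injury, and assuming the same 5% v 10% there, n per arm is 124 × 0.8 = 99 or 124 × 0.7 = 87. RR returns to 2.0, with power 0.27 or 0.24. The split recovers the contrast and most of the lost power, but power is low throughout.

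**Chance noise.** With 155 randomised per arm, the SD of the between-arm difference in the number with nerve injury is √[2 × 155 × p(1 − p)]: 8.1 at p = 0.3 and 8.8 at p = 0.5. Counting only symptomatic cases (ps = 0.21) gives √(2 × 155 × 0.21 × 0.79) = 7.2. New events per arm at p = 0.3 would be 155 × 0.0158 = 2.4 when q = 2%, and 155 × 0.158 = 24.5 when q = 20%. The noise exceeds the signal only if new events are rare.

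**The case against.** The best defence has four parts.

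- **The headings point to the repair.** Table 9 and Table 25 both label the row as a complication of tendon repair, the injury has its own place on the primary surgery form, and the CRFs, which may carry instructions, are not in these documents. This is fair as far as it goes: how sites complete the row is unknown. But Protocol 6.1 describes Table 9 as covering the condition as well as the treatments, which leaves room for recording injury-related numbness.
- **Exclusion and repair limit the problem.** Patients with both nerves divided are excluded and single nerve injuries are repaired, so later numbness or neuroma can partly reflect the operation. This stands, and is one more reason why the injury share cannot be fixed.
- **Imbalance would be visible and could be adjusted for.** Table 16 shows nerve status by arm, and a complication model would carry digital nerve injury as a covariate. The first part stands. The second is uncertain because this row is not named for modelling. Adjustment would deal with imbalance, but would not turn an old deficit into a non-event.
- **It is one descriptive secondary row in a set of example tables.** True; it does not touch the primary outcome or the non-inferiority decision.

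A reader might go further and infer that the row mostly measures the original injury, or that it cannot show surgical nerve damage. The documents do not support either. They describe nerve injury as frequent but give no number, and the result depends on assumed rates that move the share from 8% to 98%.

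**Conclusion.** The point holds as a matter of definition: the row can include deficit present before surgery, and nothing in Table 9, SAP 7.2.11 or Table 25 separates it. The size is unknown. A majority share from the injury is plausible if nerve injury is common and new events are uncommon, but it is not shown.

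The expected consequences are an inflated absolute complication rate, a between-arm ratio pulled towards 1 (2.0 to about 1.2 in the illustrations) and added chance variation. A reader might also infer a systematic bias for or against one repair. That does not follow: allocation is randomised 1:1, so nerve status at entry is balanced in expectation even without stratification.

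The trial's main conclusion is not at risk. The change is still worth making, because a stated secondary safety comparison is hard to interpret as laid out and the variable needed to clarify it is already collected.

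**What to change.** In SAP Table 25, present the nerve and sensation row separately by the nerve status on the primary surgery form: none versus partial or complete. Name the no-nerve-injury stratum as the main comparison for new nerve deficit. If the row is modelled under SAP 13.6, state that digital nerve injury is a covariate.

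The cost is a table-shell change and a sentence in SAP 7.2.11 or 13.6. It needs no new data and works for forms already completed, which matters because the SAP was signed in April 2025 with recruitment under way. The downside is smaller strata, and new damage in a digit whose nerve was already injured remains hard to classify; that stratum should be shown but read with caution.

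A rule that counts only deficits absent at surgery would look cleaner but is not feasible from these documents. Neither assessment schedule lists a baseline sensory assessment, and nerve injury seen at surgery is not the same as sensory deficit.

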7.1 Ethical Considerations and Approval

The study will be conducted to protect the human rights and dignity of the patient as reflected in the Declaration of Helsinki [39].

Formal NHS Research Ethics Committee (REC) approval will be sought via the Health Research Authority (HRA). Local R&D approvals (confirmation of capacity and capability or management approval) will be obtained for participating sites. Any further amendments to the trial protocol will be submitted and approved by the HRA and REC where required.

7.2 Competent Authority Approvals (Proposed action to comply with the Medicines for Human Use (Clinical Trials) Regulations 2004)

The study does not involve medicinal products and therefore does not require prior authorisation by the UK Competent Authority, the Medicines and Healthcare Regulatory Authority (MHRA).

The surgical techniques under investigation are well-recognised and accepted surgical procedures. The study does not involve the use of investigational medical devices or implants. We do not

Version 1.1

therefore require prior authorisation by the MHRA, under the Medical Devices Regulations (Great Britain, 2002).

7.3 Regulatory Compliance

The trial will comply with the principles of the Declaration of Helsinki [39]. It will also be conducted in compliance with the approved protocol, and the principles of GCP. An agreement will be in place between the site PI and the Sponsor, setting out respective roles and responsibilities.

All deviations from the protocol or GCP will be reported by PIs or designated site staff to YTU. The site must inform the PI as soon as they are aware of a possible serious breach of compliance, so that the sites can report this breach to the trial Sponsor (via YTU) with onward reporting to ethics and regulatory bodies as necessary. For the purposes of this regulation, a 'serious breach' is one that is likely to affect to a significant degree:

- The safety, physical or mental integrity of the participants in the trial, or
- The scientific value of the trial.

Processing of all trial data will comply with the General Data Protection Regulation (GDPR) (2016/679) (2018) and the Data Protection Act (2018).

7.4 Participant Confidentiality

The researchers and clinical care teams must ensure that participants' anonymity will be maintained and that their identities are protected from unauthorised parties. Participants will be assigned a unique identification number and this will be used on all data collection tools; participants will not be identified by their name. Sites will keep securely and maintain the participant Enrolment Log showing participant identification numbers and names of the participants.

All records will be kept in locked locations. All paper copies of consent forms will be secured safely in a separate compartment of a locked cabinet. Electronic copies will be stored separately to clinical information and access restricted to study personnel. Clinical information will not be released without written permission, except as necessary for monitoring by the trial monitors.

At the end of the study, data will be securely archived by participating sites and the University of York for a minimum of five years.

7.5 Trial Closure

The end of the trial will be defined as the last participant contact which will occur at approximately six months after the end of the recruitment period (end of follow-up for the last participant) and after all the data is entered and queries resolved.

An end of study declaration form will be submitted to the Research Ethics Committee (REC) and Sponsor within 90 days of trial completion and within 15 days if the trial is discontinued prematurely. A summary of the trial report and/or publication will be submitted to the REC, Sponsor and Funders within one year of the end of the trial.

7.6 Annual Progress Reports

An Annual Progress Report (APR) will be submitted to the REC which gave the favourable ethics opinion 12 months after the date on which the favourable opinion was given and thereafter until the end of the study (if applicable).

Version 1.1

7.7 Urgent Safety Measures

The site PI may take appropriate urgent safety measures in order to protect research participants against any immediate hazard to their health or safety. These safety measures should be taken immediately and may be taken without prior authorisation from the REC.

7.8 Indemnity

This study will be sponsored by South Tees NHS Foundation Trust. If there is negligent harm during the trial, when the NHS Trust owes a duty of care to the person harmed, NHS Indemnity covers NHS staff and medical academic staff with honorary contracts only when the trial has been approved by the R&D department.

NHS indemnity does not offer no-fault compensation and is unable to agree in advance to pay compensation for non-negligent harm.

8. Patient and Public Involvement

We will work with patient co-applicants and a patient advisory group (PAG) with lived experience of flexor tendon injuries. The aim is to secure patient and public input to the study recruitment, retention, interpretation of results and its dissemination (refer to Table 10). Our PPI strategy is focused on flexibility and limiting the burden on contributors as our patients tend to be of working age.

We will work with a co-applicant who be invited to attend (virtual) trial management group (TMG) meetings. PPI will be a standing agenda item.

They will advise on the participants' journey and play a central role in helping to develop patient communication strategies, specifically in designing the patient information to aid study recruitment and retention. They will also comment on trial findings.

A Patient Advisory Group of six people, including the patient co-applicant, will ensure wider representation of the patient population. The PAG will meet twice during study set up, twice towards the end to plan dissemination, and once a year in between. Meetings may be scheduled outside working hours to accommodate contributors. The PPI manager will liaise with contributors individually if they cannot attend.

The PPI manager will organise the PAG meeting and determine the agenda with the TMG and patient co-applicants. The PAG will review proposed solutions for any significant issues in the participants' journey. That includes presentation and wording of information for trial participants such as a patient information sheet/video, consent form and online trial information.

The PAG will lead on production of a lay trial summary for participants and general public, and contribute to the script for animation about the trial results and a press release.

PPI TRAINING AND SUPPORT

We will organise training for patient co-applications and PAG members to brief them on the trial, help them understand their role and the value of their contributions, and signpost them to resources.

Version 1.1

PPI IMPACT

The PPI manager will develop keep a spreadsheet to log PPI contributions and their influence on the project. In addition, the PAG members will be asked to fill in a feedback form after each meeting to understand how contributors feel about them and how we can make them better. keep a log of PPI contributions and their influence on the project. This work will allow the TMG, patient co-applicant and the PAG to evaluate the impact of PPI. We will report the findings in the HTA monograph.

PPI LEAD

All PPI activities will be managed and coordinated by our PPI manager who will act as the primary point of contact for PPI contributors and provide ongoing mentoring and support. The manager will also provide regular updates to contributors throughout the trial.

| Time Point | Meeting/Duties | Activity | PPI Members |
|--|---|---|---------------------|
| Ethics and Trial Set Up | Review ethics of trial processes. Review patient information documents. | Panel Meeting. Email of documents for comment. | All. |
| Mid-way through Recruitment Stage | Review of any recruitment issues. Review of any other trial issues. | Discussion with panel members on individual basis. | All. |
| Study Closure/Set Up of Full Trial | Final evaluation of any recruitment or patient issues during trial. Forward planning to improve upon full trial design. | Panel meeting | All. |
| Monthly Trial Management Meetings | Provide patient perspective on any issues or changes proposed during the course of the trial. Feedback to other panel members at panel meetings. | Either meeting attendance or via email update. | Public co-applicant |

Table 10: Patient and Public Involvement Schedule

on an ad hoc basis via email, should changes be required between scheduled meetings.

9. Finance

This research is funded by the NIHR HTA programme (Ref: 133784).

The financial arrangements for the study will be contractually agreed between the funder (HTA), and the Sponsor (South Tees NHS Foundation Trust). Separate collaboration agreements will be put in place between the Sponsor and each of the collaborating organisations.

10. Dissemination and Publication Policy

A dissemination and publication policy will be developed with an agreement between partners including ownership and exploitation of intellectual property, and publication rights. The publication policy and the agreement will ensure that any intellectual property generated during the project is protected and that the publication process is organised in a fair, balanced and transparent manner. The TMG will be responsible for overseeing these arrangements. The creation and signature of the agreements will be the responsibility of the coordinating centre (University of York). It will be ensured that all partners have input into the document.

Targets for dissemination will include NICE, Clinical Commissioning Groups, the Department of Health and the Speciality Advisory Committees (SAC) for the curriculum for clinicians who will undertake treatment of flexor tendon repairs. The study protocol and results will be presented orally and will be made publicly available in appropriate publications and a summary of the study will be made available in plain English for patient-focused outlets.

The executive summary and copy of the trial report will be sent to NICE and other relevant bodies, including Clinical Commissioning Groups, so that the study findings can inform their deliberations and be translated into clinical practice nationally. We will also work with the relevant National Clinical Director in the Department of Health to help ensure the findings of the trial are considered when implementing policy and will work with the Speciality Advisory Committees (SAC) to incorporate the findings into the training curriculum for clinicians who will undertake treatment of flexor tendon injuries. A number of dissemination channels will be used to inform clinicians, patients and the public about the results of the study. The projected outputs are listed below.

We will seek to raise the profile of the trial via social media including a dedicated Twitter account. This will be aimed at participating site staff and focus on trial progress, trial related events, and publicising research outputs.

The study protocol will be published in a peer-reviewed, open access journal, after the study commences.

A HTA monograph will be produced.

On completion of the study, the findings of the HTA report will be presented at national and international meetings such as the International Federation of Societies for Surgery of the Hand (IFSSH) and Hand Therapy (IFSHT).

